Appendix A Study Procedure Calendar

1.0 Background

Catacholaminergic Polymorphic Ventricular Tachycardia (CPVT) is an inherited arrhythmia syndrome characterized by exercise-induced ventricular arrhythmias in patients with structurally normal hearts. It is associated with a high rate of sudden cardiac death in affected patients and has a prevalence in the general population of ~1:10,000. It is caused by dysregulated intracellular calcium handling due to mutations in the gene encoding the sarcoplasmic reticulum (SR) calcium release channel (RyR2) or RyR2-binding proteins (Casq2, triadin, calmodulin). Exercise causes ventricular ectopy by exacerbating SR dysfunction due to enhanced calcium uptake from beta-adrenergic stimulation and therefore enhanced Ca leak via the RyR2 channels. Diastolic calcium leak causes delayed after depolarizations (DADs), which are a common mechanism for fatal ventricular arrhythmias.

2.0 Rationale and Specific Aims

First line therapy for CPVT is beta-blockade which is effective in many patients. Beta-blockade acts to suppress exercise-induced ectopy. However, many patients are incompletely suppressed with beta-blockade and undergo treatment with second-line therapies such as flecainide. Patients who have breakthrough arrhythmias on beta-blocker therapy may also undergo placement of an implantable cardioverter defibrillator (ICD), but ICD's do not provide complete protection against sudden cardiac death in CPVT patients due to the potential for fatal ICD storm (repeated ICDs shocks due to recurrent ventricular arrhythmias). Taken together, current therapies for CPVT are not completely effective for many affected patients and the development of alternative approaches to reducing sudden cardiac death is needed.

Recently, experimental evidence from mouse models of CPVT have demonstrated that mutations causing RyR2 dysfunction also promote sinus node dysfunction in the form of resting sinus bradycardia and/or chronotropic incompetence (an inappropriately slow sinus node rate during peak exercise). This finding is supported by observations in patients with CPVT. While it may seem that a slow heart rate would be protective for patients with CPVT because they have an exercise-induced arrhythmia, we present evidence below (section 3.0) from mouse models and human observations to support the idea that a slow sinus node rate during exercise (when catecholamine levels are high) creates an unfavorably long diastolic interval that promotes occurrence of DADs. By increasing the sinus node rate during exercise, the diastolic interval can be shortened which has been found to reduce the occurrence of DADs (and ventricular ectopy) in mice. Therefore, we aim to test the following hypothesis in humans:

Specific Aim: To test the hypothesis that increasing the sinus node rate with atropine treatment prior to exercise will reduce exercise-triggered ventricular ectopy compared to baseline in patients with CPVT.

3.0 Animal Studies and Previous Human Studies

Three studies by Kannankeril et al published in the early 2000s demonstrated that the parasympathetic nervous system exhibits demonstrable effects on cardiac electrophysiology during rest, exercise, and recovery. In the first group, parasympathetic tone was evaluated during peak exercise and recovery. 10 subjects with normal cardiac function were asked to exercise on a recumbent bike in two sessions separated by 24 hours. During the second session, subjects received atropine prior to exercise. Through serial BP, HR, and EKGs, the researchers showed a significant parasympathetic effect on cardiac electrophysiology is present throughout rest, peak exercise (although decreased), and recovery. In the second study, researchers evaluated parasympathetic effects on cardiac electrophysiology during rest, exercise, and recovery using NIPS and atropine in 9 subjects with normal LV function, intact SA or AV node (preferably both), and a dual chamber device (ICD or PM). Through a series of four sessions, a significant parasympathetic effect on sinus cycle Protocol Version #: 7 3
Protocol Date: 6/28/2016

length and AV block cycle length during rest, exercise, and recovery was revealed. Importantly, they noted that parasympathetic effect is greatest at rest, smallest during exercise, and intermediate during recovery. In the third study, parasympathetic effects were evaluated in 5 patients with LV dysfunction (EF 30-40%) and dual chamber devices (ICD or PM) capable of NIPS. The study design was similar to the second, and the results showed that parasympathetic effects on sinus cycle length and AV block are measurable during exercise and recovery. Heart disease and ventricular dysfunction decreased the parasympathetic effect on ventricular refractoriness during exercise and recovery compared to normal controls. Thus, it was concluded that parasympathetic tone does persist through exercise and recovery, and diminished parasympathetic effect on ventricular refractoriness during exercise and recovery may be responsible for the increased risk of sudden death noted during exercise and recovery. ^[1,2]

More recent studies by Faggioni et al. suggest that decreased parasympathetic tone and accelerated sinus rhythm may prevent CPVT in both mice and patients. In order to test the hypothesis that CPVT is suppressed by supraventricular overdrive stimulation, in a randomized crossover design, two CPVT mouse models (Casq2-/- and RyR2^{R4496} +/-) underwent pretreatment with either distilled water or atropine prior to catecholamine challenge with isoproterenol. Of the Casq2 -/- mice, 86% had significantly reduced ventricular arrhythmia when treated with atropine vs treatment with distilled water prior to ISO. The hypothesis was again tested using atrial overdrive pacing instead of atropine during catecholamine challenge (ISO for Casq2 - /- mice, ISO + caffeine in RyR2^{R4496} +/-mice).The atrial pacing was set to match the peak sinus rate with catecholamine challenge alone. Atrial overdrive pacing completely prevented ventricular arrhythmia in 84% of Casq2 -/- mice and 88% of RyR2^{R4496} +/- mice during catecholamine challenge with ventricular premature beats significantly reduced in both. In single myocyte studies, ventricular myocytes isolated from Casq2 -/- mice were loaded with FURa-2 AM for intracellular calcium measurements. Myocytes were then stimulated at increasing pacing rates after addin ISO. Higher pacing frequencies reduced the diastolic interval and progressively reduced the incidence of SCWs. ^[3]

Finally, a CPVT registry of patients with RyR2 mutation was screened for antiarrhythmic-naïve individuals who underwent exercise stress testing. Of the 42 drug-naïve patients with ventricular arrhythmia on exercise testing, 18 patients reached 85% of maximum predicted HR during exercise testing and exercised beyond onset of ventricular arrhythmia. These patients were included in the study. All 18 patients in the analysis developed ventricular arrhythmia by a heart rate 87% of maximum predicted heart rate. In 6 of the 18 patients, ventricular arrhythmia subsided as the sinus HR reached 89-99% of maximum predicted HR. This suggests that in a portion of CPVT patients, ventricular arrhythmia is suppressed with increasing sinus tachycardia. These studies suggest that in patients with CPVT, ventricular arrhythmia may be paradoxically suppressed by atrial tachycardia. ^[3,4]

- 1. Kannankeril PJ, Goldberger JJ Parasympathetic effects on Human Cardiac Electrophysiology During Exercise and Recovery. Am J Physiol Heart Circ Physiol. 2002; 282(6):H2091-H2098

4.0 Inclusion/Exclusion Criteria

INCLUSION	EXCLUSION
Age ≥ 6 years	Contraindication to treadmill stress testing according to Vanderbilt University Medical Center's clinical protocols (unstable angina, decompensated congestive heart failure, severe hypertension (≥ 170/90 mmHg), acute myocardial infarction (<4 days), moderate to severe aortic stenosis, acute pulmonary embolism, severe pulmonary hypertension, outflow tract obstruction, hypertrophic cardiomyopathy, left main coronary stenosis, left bundle branch block)
Able to provide written informed/consent	Females who are pregnant
Clinical diagnosis of Catacholaminergic Polymorphic Ventricular Tachycardia	In the judgement of the investigator, any clinically significant ongoing medical or surgical condition that might jeopardize the subject's safety or interfere with the conduct of the study
Able to exercise on a treadmill	

5.0 Enrollment/Randomization

For feasibility considerations, this pilot study will be non-randomized. Reasons include: i.) administration of atropine before the first exercise portion would require a 2-day protocol for complete drug-washout; ii) administration of atropine results in symptomatic palpitations and in prior studies increases the rate of voluntary participant withdrawal.

6.0 Study Procedures

General Approach: This is a prospective cross-over trial that will enroll eligible patients with CPVT and perform a baseline treadmill exercise tolerance test (ETT) followed by a repeat treadmill ETT with I.V. atropine administered immediately prior to exercise. Atropine is a parasympathetic blocker and results in sinus tachycardia, which is expected to reduce the diastolic interval thereby reducing delayed after depolarizations and ventricular ectopy compared to baseline. Both ETTs will be performed on the same day with two hours of rest scheduled between ETTs. The primary analysis will be a paired comparison of the number of ventricular ectopic beats recorded during exercise (and recovery) at baseline and following pre-treatment with atropine. Secondary endpoints will include the presence of ventricular ectopy (yes/no), complex ventricular ectopy (couplets or greater, yes/no), and the number of runs of complex ventricular ectopy.

Prior to Enrollment	Patient recruited in clinic or by phone
	Patient will continue all outpatient medications prior to study. Specifically, beta-blocker therapy will not be stopped for this study.
Day 1	
8:00 AM	Arrive to Clinical Research Center (CRC)
	Sign consent forms
8:15 AM	Place peripheral I.V.

8:30 AM	Interrogate Device (ICD) (if ICD present)
0100741	Reprogram therapy detection zones if needed
8:45 AM	Place electrodes for ETT
0110741	
Part 1	Baseline Exercise Tolerance Test (ETT)
	Blood pressure, 12-lead ECG
8:50 AM	Start Treadmill ETT (Standard Bruce Protocol, max time=21 minutes)
	Stage 1 (1.7 mph, 10% grade, 3 mins)
8:53 AM	(if necessary) Begin Stage 2 (2.5 mph, 12% grade, 3 mins)
8:56 AM	(if necessary) Begin Stage 3 (3.4 mph, 14% grade, 3 mins)
8:59 AM	(if necessary) Begin Stage 4 (4.2 mph, 16% grade, 3 mins)
9:02 AM	(if necessary) Begin Stage 5 (5.0 mph, 18% grade, 3 mins)
9:05 AM	(if necessary) Begin Stage 6 (5.5 mph, 20% grade, 3 mins)
9:08 AM	(if necessary) Begin Stage 7 (6.0 mph, 22% grade, 3 mins)
+0:20 mins	Monitored rest recovery period
+2:00 hours	Unmonitored rest period. Patient remains on the CRC
Part 2	Atropine Pre-treatment Treadmill Exercise Tolerance Test
11:00 AM	Blood pressure, 12-lead ECG
11:05 AM	Give Atropine (0.04 mg/kg up to max of 3 mg I.V.)
	Start ETT (Standard Bruce Protocol, max time=21 minutes)
	Stage 1 (1.7 mph, 10% grade, 3 mins)
11:08 AM	(if necessary) Begin Stage 2 (2.5 mph, 12% grade, 3 mins)
11:11 AM	(if necessary) Begin Stage 3 (3.4 mph, 14% grade, 3 mins)
11:14 AM	(if necessary) Begin Stage 4 (4.2 mph, 16% grade, 3 mins)
11:17 AM	(if necessary) Begin Stage 5 (5.0 mph, 18% grade, 3 mins)
11:20 AM	(if necessary) Begin Stage 6 (5.5 mph, 20% grade, 3 mins)
11:23 AM	(if necessary) Begin Stage 7 (6.0 mph, 22% grade, 3 mins)
+0:20 mins	Monitored rest recovery period
Find of	
End of Study	
+4:00 hours	Discharge home after 4 hours of observation
	Erase arrhythmia counters on device and reprogram any changes made to therapy
	detection zones
	Disconnect from monitor and remove electrodes
	Remove peripheral I.V.
	Discharged from CRC

Exercise Tolerance Test (ETT)

The ETT protocol is adapted from the clinical protocol used at the Vanderbilt Heart and Vascular Institute. The participant will be asked to not eat or drink for 4 hours prior to each session, except for a small amount of water used to take necessary meds. He/she will be instructed to take all medication as prescribed prior to the test. Participants will be instructed to wear clothing and shoes appropriate for exercising on a treadmill. An IV will be placed in order to deliver medication during the testing. For a patient with an ICD, the patient's ICD will be interrogated, and reprogrammed if necessary. Electrodes will be placed for ETT.

The patient will be instructed to stand on the treadmill, and will be asked to begin walking on the treadmill using Bruce protocol. The patient will be encouraged to maintain a minimum heart rate of 85% of his/her age predicted maximum. He/She will be encouraged to walk/run until the end of their comfort zone unless the supervising professional terminates the test before then. The exercise portion of the study is planned to last a maximum of 21 minutes per session. The two sessions will be separated by a 20 minute

supervised rest period followed by a 2 hour unsupervised rest period where the patient will be asked to remain at the CRC. After the second exercise session, a 4+ hour observation period will begin. For a patient with an ICD, any changes to ICD settings will be reprogrammed to previous settings. The patient will be disconnected from monitors and electrodes, and the peripheral IV will be removed. In total, the total time commitment is approximately 8 consecutive hours. The medication used during the testing may cause discomfort or an unpleasant sensation.

Exercise will be terminated prior to the end of the test under the following circumstances:

- Inability to exercise
- Marked exercise-induced hypotension (Decrease in Systolic Blood Pressure >10 mmHg despite increased workload)
- Hypertensive response (Systolic Blood Pressure >230 mmHg and/or Diastolic Blood Pressure > 115 mmHg).
- Sustained ventricular tachycardia
- Development of LBBB or intraventricular conduction delay that cannot be distinguished from ventricular tachycardia
- ST segment depression > 2 mm or ST elevation >1 mm in leads without diagnostic Q waves (except leads V1 or aVR)
- Moderate to severe angina pectoris
- Marked dyspnea or fatigue
- Ataxia, dizziness, or near syncope
- Signs of poor perfusion
- Technical difficulties in monitoring the ECG or systolic blood pressure

At the end of the exercise protocol, the recovery phase will begin. The first phase of recovery is a cooldown phase with the patient walking on the treadmill. The patient will be stopped after 2 minutes, and the patient will be asked to lay supine for the remainder of the recovery period.

Blood pressure, HR, and EKG tracings will be recorded throughout the exercise and recovery period, with patient either walking/running or laying in supine position.

Each patient will be tested individually. There will be no videotaping or audiotaping.

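### A patient whose ICD detection zones are changed before the baseline test spends the unmonitored 1.5 to 2 hour rest between tests with altered detection

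*Combined protocol and SAP*

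**What the plan says.** The schedule table in Section 6.0 has an 8:30 AM step for patients with an ICD: interrogate the device and "Reprogram therapy detection zones if needed". The baseline test starts at 8:50 AM, lasts at most 21 minutes, and is followed by 20 minutes of monitored recovery. The next row is two hours long and reads "Unmonitored rest period. Patient remains on the CRC". The Exercise Tolerance Test text in the same section agrees, describing a 20-minute "supervised rest period followed by a 2 hour unsupervised rest period where the patient will be asked to remain at the CRC". Part 2 opens at 11:00 AM, with atropine at 11:05 AM.

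Restoration of the device appears twice, both times after the second test. In the table it is under End of Study: "Erase arrhythmia counters on device and reprogram any changes made to therapy" detection zones. In the text, the sentence "After the second exercise session, a 4+ hour observation period will begin" is followed by "For a patient with an ICD, any changes to ICD settings will be reprogrammed to previous settings", with no clock time.

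Section 7.0 requires continuous cardiac monitoring after the exercise test for 20 minutes, or longer if ectopy has not yet returned to baseline.

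**The concern.** The trial deliberately exercises patients with an exercise-induced arrhythmia, and Section 7.0 describes ventricular arrhythmia as expected under the protocol. If a patient's ICD no longer detects arrhythmia as it was set up to, ECG monitoring is the natural substitute. The plan provides that substitute during exercise and early recovery, then stops it for the rest between tests while the device remains changed.

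The people concerned may not be the lowest-risk participants. Section 2.0 says that patients with breakthrough arrhythmia on beta-blockers may receive an ICD. At stake is delayed recognition of a ventricular arrhythmia during the rest.

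**Working it through.** **Sequence.** Following Section 6.0 in order for a patient with an ICD:

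| Step | ICD zones | ECG monitoring |
|---|---|---|
| 8:30 AM, device check | changed if needed | electrodes placed at 8:45 AM |
| Baseline test from 8:50 AM | changed | yes |
| 20-minute recovery | changed | yes |
| Rest between tests | changed; no restoring step | no |
| Part 2 from 11:00 AM | changed | yes |
| After the second test | restored (table: End of Study; text: no time given) | observation; see objection |

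The rest is the only row where changed zones coincide with an explicit absence of monitoring.

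**Length of the rest.** The stated figure, in both table and text, is 2 hours. The table's clock times can be checked against it:

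rest = 11:00 − (8:50 + exercise minutes + 20 minutes of recovery)

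- Full 21-minute test: 8:50 + 21 + 20 = 9:31, and 11:00 − 9:31 = 89 minutes, about 1.5 hours.
- Test of 3 minutes (one stage): 8:50 + 3 + 20 = 9:13, and 11:00 − 9:13 = 107 minutes, about 1.8 hours.
- A full 2-hour rest would instead start Part 2 at 11:13 (3-minute test) to 11:31 (21-minute test).

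The clock times therefore do not reproduce the stated 2 hours exactly, and a range of roughly 1.5 to 2 hours covers both readings. If monitoring is prolonged because ectopy persists, the rest starts later. It is shorter only if Part 2 still begins at 11:00.

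**Reprogrammings per affected patient.**

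- As written: change, restore = 2.
- With ECG monitoring through the rest: change, restore = 2, so none extra.
- With restoration for the rest: change, restore, change, restore = 4, so 2 extra.

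These figures size the interval and the burden of the remedies. They do not size the risk: the documents do not give the number of patients with an ICD, how often zones are changed, or by how much.

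**The case against.** The strongest reply is that the hazard is conjectural and the gap already has safeguards. The plan speaks of detection zones changed only where needed. It never says therapy is switched off, and Section 7.0 lists ICD shock among unexpected findings, which fits a device that can still act. If the Section 7.0 monitoring rule covers both tests, as its wording suggests, a patient enters the rest only once ectopy is back to baseline. The patient is then resting, before any atropine, on usual medication, with an IV in place and on the unit. Exercise stops for sustained ventricular tachycardia. Section 7.0 also says all included patients have completed at least two stress tests without adverse events.

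Most of this stands, and it lowers the likely risk. It does not close the gap: returning to baseline at the start of the rest does not detect an event later in it. The history of uneventful tests is not a criterion in Section 4.0, and nothing says those tests were done with changed zones.

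Three stronger readings are tempting, and the documents support none of them.

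- A reader might infer that ICD protection is lost during the rest. The extent of the change is not stated, so this is possible but not shown.
- A reader might contrast the unmonitored rest with more than 4 hours of ECG monitoring after the second test under the same device settings. The plan calls that period observation, not continuous ECG. The table row "Disconnect from monitor and remove electrodes" hints at monitoring, but that block lists discharge first and is not a strict sequence. The text does not fix restoration after the observation period, and atropine is a separate reason for observing longer.
- A reader might infer that only the ICD could reveal an arrhythmia during the rest. A patient on the unit can report symptoms, and the documents give no staffing details either way.

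**Conclusion.** The point holds as a minor to moderate safety matter. As written, a patient whose zones were changed spends about 89 minutes to 2 hours between tests with altered detection and neither ECG monitoring nor supervision. Table and text agree on each element, so this is not one stray word.

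The conclusion rests on two conditions. First, zones are actually changed in some patients; the plan makes this conditional and gives no frequency. Second, the Appendix A calendar, which is named but was not in the supplied text, contains no interim restoration or monitoring step; that should be checked.

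The probability of an event in the gap is unknown and probably low. The case for acting is that the possible consequence is grave and the remedy is cheap. The primary analysis is not affected: it compares ectopic beats during exercise and recovery, and the rest falls outside both.

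**What to change.** Add one sentence to Section 6.0: any patient whose ICD detection zones were changed stays on continuous ECG monitoring, using the electrodes already placed, until the settings are restored.

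The alternative is to restore the settings before the rest and change them again before Part 2. This ranks second because its two extra reprogrammings per affected patient are each a chance of error.

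The cost of the first option is up to about 2 more hours of monitoring between tests, for that subset only. It assumes that existing unit staff can watch the monitor and that monitoring equipment is available during the rest; the documents confirm neither. The table lists electrode placement once and removal once, so no second placement appears necessary. Visit length is unchanged, since the patient already stays on site and "the total time commitment is approximately 8 consecutive hours". If the observation after the second test is not already on ECG, the sentence would extend monitoring there too. Restoring the settings early in that observation, which the text permits, would keep this short.

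### The only numeric effort cue in both exercise tests is a heart rate that atropine itself raises, and nothing matches workload or duration behind the raw ectopy count

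*Combined protocol and SAP*

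**What the plan says.** Section 6.0 (Exercise Tolerance Test) gives two effort instructions, the same for both tests. The first is numeric: "The patient will be encouraged to maintain a minimum heart rate of 85% of his/her age predicted maximum". The second is not: "He/She will be encouraged to walk/run until the end of their comfort zone unless the supervising professional terminates the test before then". There is also a ceiling: "The exercise portion of the study is planned to last a maximum of 21 minutes per session". The schedule table lists seven Bruce stages of 3 minutes, and Stages 2 to 7 carry a conditional label, as in "if necessary) Begin Stage 2 (2.5 mph, 12% grade, 3 mins". The condition is not defined. Reaching 85% is not among the termination criteria.

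The General Approach in the same section describes the intervention: "Atropine is a parasympathetic blocker and results in sinus tachycardia". Section 5.0 makes the study non-randomised, so the untreated test always comes first. No blinding of the staff who encourage the patient is described.

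The primary endpoint (Sections 6.0 and 10.0) is the number of ectopic beats over exercise and recovery, compared within patients by a signed-rank test at 0.05. Neither section describes matching, normalising or adjusting for stage reached, exercise time or achieved heart rate. Heart rate is recorded throughout both tests.

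**The concern.** A heart-rate cue is a fair guide to effort only if heart rate relates to workload in the same way in both tests. Here the drug is given to change that relation. Section 2.0 says that CPVT may bring "chronotropic incompetence (an inappropriately slow sinus node rate during peak exercise", and Section 6.0 keeps patients on their beta-blockers. Such a patient may sit below 85% for much of the baseline test and be urged on. After atropine the same patient may pass 85% at a lower workload, and the numeric reason to urge further is gone.

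If encouragement follows the cue in this way, the second test involves less exercise and so fewer opportunities for ectopy. Because the order is fixed, the difference always runs one way, towards the hypothesis. It would be counted as a drug effect, and it would carry into the effect size that Section 10.0 wants for planning later trials.

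**Working it through.** The plan gives no sample size, power or expected effect, so it has no figure to reproduce. The checks below ask whether the cue moves with treatment, and what an effort difference would do to the count.

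**1. Does atropine move the cue?** Yes in direction, by Section 6.0. The size during exercise is not given. Section 3.0 says of earlier work that the "parasympathetic effect is greatest at rest, smallest during exercise, and intermediate during recovery", which argues for a modest shift.

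**2. How much sooner could the cue be met?** Assumed inputs, not from the documents: heart rate rises 8 to 12 bpm per Bruce minute, and atropine adds 10 to 30 bpm.
- Time gained = added bpm / bpm per minute.
- Smallest: 10/12 = 0.8 min. Largest: 30/8 = 3.75 min, or about 3.8 min.
- At the low end of the drug effect (10 bpm): 10/12 = 0.8 to 10/8 = 1.25 min.

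This is time to reach 85%. It is not a difference in exercise duration, because the patient is asked to continue past it.

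**3. What would a shorter second test do to the raw count?** Assume no drug effect and a constant ectopy rate. Let T be the baseline exercise time (9, 12 or 15 min, assumed) and k the number of 3-minute stages lost. Recovery is taken as the 20 minutes in the schedule.
- Ectopy only in exercise: ratio = (T - 3k)/T.
- Ectopy spread evenly over exercise and recovery: ratio = (T - 3k + 20)/(T + 20).

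| T (min) | k | Exercise only | Exercise + 20 min recovery |
|---|---|---|---|
| 9 | 1 | 6/9 = 67% | 26/29 = 90% |
| 12 | 1 | 9/12 = 75% | 29/32 = 91% |
| 15 | 1 | 12/15 = 80% | 32/35 = 91% |
| 9 | 2 | 3/9 = 33% | 23/29 = 79% |
| 12 | 2 | 6/12 = 50% | 26/32 = 81% |
| 15 | 2 | 9/15 = 60% | 29/35 = 83% |

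If ectopy is concentrated in the last stages, the fall is larger than the constant-rate figures show.

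**4. Would a small, consistent fall matter to the test?** A signed-rank test responds to consistent direction. If all n untied pairs fall, the exact two-sided p-value is 2 × (1/2)^n:
- n = 5: 2 × 1/32 = 0.063.
- n = 6: 2 × 1/64 = 0.031, however small each fall is.

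The plan does not state sidedness or sample size, so six is only an illustration.

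**The case against.** The strongest reply is that 85% is a minimum. The next sentence of the plan asks every patient, in both tests, to go on to the limit of comfort, and no rule says that urging stops at 85%. The conditional stage label is never tied to heart rate and may only mean that the patient is still exercising. The bias therefore depends on staff behaviour that the plan does not prescribe.

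Most of this stands. It makes the bias possible rather than built in, and it rules out calling 85% the sole effort target. It does not secure equal effort. The comfort instruction has no workload anchor, and comfort may itself change with the drug: Section 5.0 says that atropine causes palpitations and has increased voluntary withdrawal.

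A reader might also infer that the cue makes a null result unreadable, because Section 3.0 reports: "In 6 of the 18 patients, ventricular arrhythmia subsided as the sinus HR reached 89-99% of maximum predicted HR". The documents do not support that.
- Those 18 were drug-naive registry patients, not participants in this trial, and 6 of 18 (33%; exact 95% interval 13% to 59%) is thin evidence for a threshold.
- A floor of 85% keeps nobody below 89%. One figure is a past observation and the other a minimum, so they do not contradict each other.
- Heart rate is recorded, so the range reached can be checked, and Section 10.0 already concedes that the pilot may be underpowered.

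**Conclusion.** The point holds as a risk to a positive result. The one numeric effort cue moves with the treatment, the order is fixed, no blinding is described, and the endpoint is a raw count with no protection against unequal workload or duration. Any easing of encouragement after atropine would look like benefit.

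Its size cannot be derived from the documents. Under the constant-rate illustration, one stage less gives 67-80% of the baseline count (exercise only) or 90-91% (with 20 minutes of recovery), with no drug effect at all. These figures rest on the assumed baseline times and on the second test actually ending a stage earlier, which the plan neither requires nor prevents. The 0.8 to 3.8 minutes in step 2 should not be read as that shortfall.

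This should be changed, because the change is cheap and the pilot exists to supply an effect size. It does not invalidate the design.

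**What to change.** **Section 6.0.** Use the same scripted encouragement in both tests, timed by stage or minute and not by achieved heart rate. Leave all termination criteria as they are. How the 85% figure is kept, or reconciled with the script, is an exercise instruction for the investigator to decide.

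**Section 10.0.** Report stage reached, exercise duration and peak heart rate (percent of predicted) for each test. Prespecify one supportive paired comparison: ectopic beats over the stages completed in both tests, or beats per minute. The matched-stage form is cleaner if ectopy rises with workload. Match on workload and not on heart rate, since a faster rate is the proposed mechanism. Achieved heart rate may be described when a null is interpreted. Do not define a subset by heart rate reached after atropine: that selects patients on something the drug changes.

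**Cost.** A few sentences, using heart rates already recorded and stages already timed. The matched-stage comparison discards beats from unmatched stages and from recovery, and the set of shared stages is itself fixed after treatment, so it supports the primary analysis and does not replace it.
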